Research Question

How do different ketone supplement types affect blood beta-hydroxybutyrate $(\beta\text{-OHB})$ and blood glucose in healthy individuals?

Objectives

- a) To determine the effect of acute ketone supplementation on blood β -OHB across different types of ketone supplements.
- b) To compare changes in blood glucose following acute supplementation with different types of ketone supplements.
- c) To evaluate the influence of acute ketone supplementation on blood pressure and heart rate across different types of ketone supplements.
- d) To investigate the effect of acute supplementation with different ketone supplements on gastrointestinal discomfort, hunger, and fullness.
- e) To explore supplement acceptability and taste across different ketone supplements.

Hypotheses

- a) All ketone supplements will raise blood β -OHB.
- b) All ketone supplements will lower blood glucose.

This is an exploratory/descriptive pilot study that is designed to inform future research; therefore, we do not pose specific hypotheses as to how the ketone supplements will differ with respect to their effects on the above-outlined objectives.

Background Information

Acute increases in blood ketones (beta-hydroxybutyrate, β -OHB) have been found to temporarily reduce blood glucose [1] but therapeutic application has traditionally been limited due to the need for ketone infusion or severe dietary restrictions to achieve nutritional ketosis. With the recent development of exogenous ketone supplements that can be consumed orally [2], it is now possible to acutely raise blood β -OHB concentration without the need for other nutritional modifications or invasive procedures. In our lab, we have previously shown that acute ingestion of oral ketone supplements potently increases β -OHB and immediately lowers blood glucose [3-6]. These findings suggest exogenous ketones to be a promising therapeutic strategy aimed at lowering blood glucose and improving blood glucose control in individuals with impaired glucose metabolism, particularly individuals with prediabetes or type 2 diabetes [7].

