The first ketone supplements available on the market were in the form of either ketone salts (i.e., β -OHB bound to a mineral salt) or ketone monoesters (i.e., β -OHB bound to a ketone precursor such as butanediol) [2]. Ketone salts can lead to gastrointestinal discomfort in many individuals [8] and ketone monoesters have an extremely unpleasant bitter taste. This makes adherence to a nutritional supplement regimen using ketone salts or monoesters challenging. Since then, new formulations have been developed that differ with respect to ingredients (e.g., include flavouring to mask the bitter taste and improve palatability) and chemical properties (e.g., different precursors and/or types of molecule the β -OHB is bound to). In particular, two new ketone supplements (beta-hydroxybutyric acid and 1,3-Butanediol) have recently become commercially available that promise an improved consumer experience.

However, little is known about the pharmacokinetics of these supplements, which can be expected to differ from the original supplements based on differences in formulation. This, in turn, may affect the glucose-lowering properties of the exogenous ketone supplements. While qualities such as an improved taste and gastrointestinal tolerability are desirable in ketone supplements, it is of importance for the field of research focusing on the therapeutic value of exogenous ketones to establish the effect of these different ketone supplements on blood β -OHB and blood glucose and determine how they compare to the effects of the by now well-established ketone monoester.

The overall aim of this pilot study is therefore to test the β -OHB-raising and glucose-lowering effect of these two new types of commercially-available oral ketone supplements (beta-hydroxybutyric acid and 1,3-Butanediol) in comparison to a ketone monoester, which we have used in our previous studies on ketone supplementation.

Research Method

Experimental design

A double-blind randomized cross-over pilot study in which N = 12 healthy adults will participate in three experimental trials with a different ketone supplement in each trial. Each ketone supplement has FDA GRAS (Generally Recognized As Safe) status as a food additive and is available for online purchase in Canada:

- 1) "KE4" (by KetoneAid)
 - Beta-hydroxybutyrate monoester
- 2) "Kenetik" (by DrinkKenetik)
 - Beta-hydroxybutyric acid
- 3) "Ketone 2.0" (by HVMN)
 - 1,3-Butanediol

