All participants will provide written informed consent before start of data collection. Following screening and informed consent, eligible participants will participate in three experimental trials of β -OHB supplementation with the order of treatment randomized, balanced, and separated by at least 48 hours. Pre-menopausal women will be tested in the follicular phase (days 3-9) to minimize any potential changes in insulin sensitivity across the menstrual cycle [9]. Participants will be asked to refrain from structured exercise and alcohol on the day before each trial. Furthermore, participants will be instructed to record their dietary intake on the day prior to their first experimental visit, and to consume the same foods and quantities on the days before the subsequent experimental visits. Participants will then be asked to fast overnight (at least 8 hours) and refrain from taking any medications on the morning of the trial.

Upon arrival, a baseline fasting blood sample will be obtained via finger prick. The oral ketone supplement will then be consumed within 5 minutes. The different

supplement types will have an overall similar yet likely distinguishable flavour and will be provided at different volumes (based on the manufacturer's formulation) – however, participants will not be aware which flavour and volume will correspond to which ketone supplement. Furthermore, all supplements will be provided in opaque plastic bottles (labelled with "A", "B", or "C" according to a code that only the principal investigator has access to) such that neither the participant nor the research lead will be able to visually identify the supplement type. Each ketone supplement will be provided at a dose of 10 g active ingredient (i.e., 10 g of betahydroxybutyrate monoester, betahydroxybutyric acid, or 1,3-Butanediol). This is the recommended serving size for the two new ketone supplements to be tested (betahydroxybutyric acid and 1,3-Butanediol) and is in line with a previous pharmacokinetic study that showed a dose of \sim 10 g betahydroxybutyrate monoester to successfully raise β -OHB within 30 minutes [2]. Specifically, this leads to one trial each with:

- 1) 20 mL of "KE4" (i.e.,10 g beta-hydroxybutyrate monoester)
- 2) 237 mL of "Kenetik" (i.e., 10 g beta-hydroxybutyric acid)
- 3) 35 mL of "Ketone 2.0" (i.e., 10 g 1,3-Butanediol)

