The primary outcome will be total β -OHB as represented by the area under the curve across 4 hours. Secondary outcomes include blood glucose, blood pressure, heart rate, taste and supplement acceptability, hunger and fullness, and gastrointestinal tolerability - all measured across the 240-minute post-supplementation period. Blood samples will be collected via finger prick; blood β -OHB and glucose levels will be measured using the "Keto-Mojo" handheld monitor at baseline and 15, 30, 60, 90, 120, 180, and 240 minutes after ingestion of the ketone supplement.

Visits Summary

The study will involve a total of 3 visits to the laboratory.

Visit 1: Baseline screening & first experimental trial (duration 270 minutes)

Individuals will be recruited by word-of-mouth. Individuals must be able to read and understand English in order to understand the study instructions. On the initial visit, the potential participant will read through the information and consent form, be able to ask any questions, and provide written informed consent. The research lead ([name] Candidate) will ensure that the participant understands the details of the study and consent form.

Inclusion criteria will be: i) over the age of 18; and ii) able to fast overnight. **Exclusion criteria** will include: i) being a competitive endurance athlete; ii) following a ketogenic diet, low-calorie diet, periodic fasting regimen, or regularly consuming ketogenic supplements; iii) being unable to travel to and from the university; iv) being unable to follow the diet instructions; v) being pregnant or planning to become pregnant during the study; vi) having been diagnosed with a chronic disorder of glucose or fat metabolism, including type 2 diabetes, chronic pancreatitis, or gallbladder disease; vii) being unable to read or communicate in English.

Females will complete the menstrual cycle questionnaire to confirm they are in the follicular phase. Anthropometric and physiologic measurements will be collected (height, body weight, waist circumferences, blood pressure) for baseline participant characterization. The research lead will review the dietary record with the participant and confirm the participant is fasted and has refrained from structured exercise and alcohol the day prior.

A baseline finger prick will then be performed before ingestion of the ketone supplement. Another 7 finger pricks will be performed at 15, 30, 60, 90, 120, 180,

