and 240 minutes after ingestion of the supplement. Throughout the 240-minute period, participants will be allowed to do quiet work or perform other sedentary activities (reading, watching a movie). Participants will be asked to complete the questionnaire on gastrointestinal discomfort 60 minutes after ingestion of the supplement, and the questionnaires on hunger and fullness as well as taste and supplement acceptability at the end of the 240-minute post-supplementation period.

At the end of the visit, the participant will be reminded to consume the same diet on the day before the next experimental trial, and to refrain from structured exercise and alcohol consumption in the 24 hours prior.

Visits 2 & 3: Second and third experimental trial (duration 240 minutes)

The second and third experimental trial will be identical to the first visit (except no baseline anthropometric measurements will be performed), with the only difference being the different ketone supplement provided to the participant.

Statistical Analyses

Descriptive statistics (means, SD, and frequencies) will be calculated. Significance will be set at P < 0.05. Data across time will be analyzed in R using a linear mixed effects model with subjects as a random factor and condition and time as fixed factors. Assumptions will be tested using Q-Q plots of residuals. Data with skewed distributions will be log-transformed or non-linear mixed effects models will be used. All participants will be included in the intention-to-treat (ITT) analyses and missing data will not be imputed, per contemporary guidelines with use of linear mixed models [10].

Sample Size

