We will recruit 12 participants to be included in this cross-over study, which has blood β-OHB (as represented by the area under the curve across the 4 hours following ingestion of the supplement) as the primary outcome. A previous pharmacokinetic study exploring the effects of a ketone monoester provided at a dose of \sim 10 g in healthy adults found that blood β -OHB was raised to 1.4 \pm 0.6 mM within 30 minutes, and to an average of 0.5 ± 0.5 mM across the entire 4-hour post-supplementation period [2], which represents an effect size of d > 1.0compared to baseline. Using the outcome data from this study (N = 15) and assuming 80% power with an alpha level of 0.05 and a moderate correlation between repeated measures of 0.5, a total sample size of N = 6 would be sufficient to detect an increase in average blood β-OHB compared to baseline (calculated using G*Power v3.1). In order to allow for a more nuanced evaluation of differences between ketone supplements and to account for any dropouts or missing blood samples, we will recruit 12 participants (aiming for equal males and females), which is in line with the sample size of previous pharmacokinetic studies of ketone supplements [2].

Significance

The results of this study will help determine the effect of different types of ketone supplements on blood β -OHB and glucose. This is a pilot study and it will provide useful data to better answer future research questions and aid in the design of longer-term studies.

Outcome Measurements and Methods

The primary outcome will be total β -OHB as represented by the area under the curve across 4 hours. Secondary outcomes include blood glucose, blood pressure, heart rate, hunger and fullness, gastrointestinal discomfort, and taste and supplement acceptability.

Anthropometric Measures

Waist circumference (cm), height (cm), and weight (kg) will be measured using standard procedures. Body mass index (BMI) will be calculated as kg/m².

Physiological Measures

Resting blood pressure and heart rate will be collected for descriptive purpose and throughout the study visits (at the same time points as blood samples are collected). Before measurements, participants will be instructed to sit quietly and rest for 5 minutes. A finger tip heart rate monitor will track heart rate. Blood pressure will be collected using a cuff around the upper arm, a stethoscope will be placed in the cubital fossa for systolic and diastolic blood pressure.

Blood Sampling

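### Hunger, fullness and GI discomfort are rated only after the drink and there is no supplement-free visit, so change from the pre-drink state cannot be estimated for objective (d)

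*Combined protocol and SAP*

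**What the plan says.** Objective (d) is "To investigate the effect of acute supplementation with different ketone supplements on gastrointestinal discomfort, hunger, and fullness". Visits Summary (Visit 1) fixes the rating times. Participants "complete the questionnaire on gastrointestinal discomfort 60 minutes after ingestion of the supplement", and complete "the questionnaires on hunger and fullness as well as taste and supplement acceptability at the end of the 240-minute post-supplementation period". Visits 2 and 3 repeat this schedule apart from the anthropometry and the supplement given.

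Research Method describes the secondary outcomes as "all measured across the 240-minute post-supplementation period". That fits poorly with single ratings and names no baseline.

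The other outcomes do have a pre-drink value. For blood, "A baseline finger prick will then be performed before ingestion of the ketone supplement". Blood pressure and heart rate are taken "at the same time points as blood samples are collected", which includes baseline.

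The design is "three experimental trials with a different ketone supplement in each trial", "with the order of treatment randomized, balanced, and separated by at least 48 hours". All three conditions are active ketone products. Statistical Analyses plans a mixed model with subject as a random factor and condition and time as fixed factors. It names no baseline covariate.

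**The concern.** An effect of supplementation on a symptom or appetite score needs a reference: either the same person's rating before the drink or a visit without a supplement. For hunger, fullness and GI discomfort the plan has neither. If all three products raised GI discomfort by the same amount, the data would look the same as if none did. With one rating per visit, the model's time factor also has nothing to estimate for these outcomes, and no later analysis can recover a rating that was not taken.

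The second consequence is for precision. How hungry or unsettled a person arrives varies from visit to visit. Without a pre-drink rating, that variation stays in the error of the between-supplement comparison. GI tolerability is part of the stated motivation for the new products, and the pilot is meant to inform longer studies, which would benefit from change estimates and a pre/post correlation.

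**Working it through.** **1. Is there a reference value?** Setting the sections side by side:

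| Outcome | Pre-drink value | Post-drink values | Supplement-free visit |
|---|---|---|---|
| β-OHB, glucose | yes | 15 to 240 min (7) | no |
| Blood pressure, heart rate | yes, same times as blood | 15 to 240 min (7) | no |
| GI discomfort | none | 60 min (1) | no |
| Hunger, fullness | none | 240 min (1) | no |

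Taste and acceptability cannot be rated before the drink, so they are not part of this point.

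**2. Is there a planned figure to reproduce?** Not for these outcomes. The N = 6 calculation in Sample Size concerns the rise in β-OHB over baseline, and its assumed correlation of 0.5 belongs to that outcome. No SD or pre/post correlation is given for the questionnaires, so r below is an assumption shown over a range.

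**3. Bias or noise?** Inputs: 12 people, each rated under every supplement; visit-to-visit SD of 1 for both pre- and post-drink ratings; within-visit correlation r; starting state independent of the supplement, as randomization implies. The standard error of a pairwise post-only contrast is √(2/12) = 0.41 SD. In 20,000 simulated trials per setting with no true difference, the mean contrast lay within 0.005 of zero and the type I error was 4.8% to 5.3% at every r from 0 to 0.7. Starting state adds noise and does not bias the contrast.

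**4. How much noise?** Starting state makes up r² of the post-only contrast variance: 0.3² = 9%, 0.5² = 25%, 0.7² = 49%. Relative to post-only, the contrast variance is 1 − r² with a covariate (before the cost of estimating its slope) and 2(1 − r) with a plain change score. The latter is 1.4, 1.0 and 0.6 at r = 0.3, 0.5 and 0.7, so a change score is worse than no baseline at all when r is below 0.5.

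Simulated power for a true difference of 1 visit-to-visit SD, two-sided 5%, one pair of supplements:

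| r | Post-only (as planned) | Pre-drink covariate | Plain change score |
|---|---|---|---|
| 0 | 60% | 55% | 35% |
| 0.3 | 60% | 60% | 47% |
| 0.5 | 60% | 68% | 60% |
| 0.7 | 60% | 83% | 82% |

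Using all three visits in one model gives (12 − 1) × (3 − 1) = 22 error df, or 21 with the covariate. Power is then about 65% without the covariate and about 66%, 75% and 89% with it at r = 0.3, 0.5 and 0.7. At r = 0 the covariate costs about 2 percentage points. The pattern is the same.

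**5. What would a pre-drink rating measure?** The minimum fast is 8 hours, so at the 240-minute rating a participant has gone at least 8 + 4 = 12 hours without food. A change in hunger from 0 to 240 minutes combines any supplement effect with four more hours of fasting.

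**The case against.** The strongest reply is that objective (d) is comparative. The overall aim is to compare two new products with the monoester, and the only directional hypotheses are for β-OHB and glucose. A paired difference in post-drink ratings, with its confidence interval, answers that question without a baseline. Starting state is also partly standardised by the overnight fast, the repeated previous-day diet, and the avoidance of structured exercise and alcohol. All of this stands.

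It rules out two stronger readings. A reader might infer that each visit's starting state will be mistaken for a supplement difference. The documents do not support that: order is randomized and balanced, every person takes all three products, and chance differences in starting state are already covered by the standard error. A reader might also infer that objective (d) cannot be answered at all. Its between-supplement part can be.

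Three further points are fair. A pre-drink rating does not isolate a supplement's effect, because without a control visit the change also contains elapsed time and fasting. The precision gain is of unknown size. Fasted healthy adults may report little GI discomfort before the drink (an assumption), which would leave a covariate little to explain. The questionnaires are not reproduced, so whether the GI items suit a pre-drink rating cannot be checked. These limit the benefit, but they do not supply the missing reference value.

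**Conclusion.** The point holds in a limited form. As written, the trial cannot estimate change from the pre-drink state in hunger, fullness or GI discomfort under any supplement. This follows from the visit schedule and needs no assumption. Between-supplement comparisons remain valid, given balanced order and no carryover, with a loss of precision that depends on r. On the assumptions above, a pre-drink covariate gives about no gain in power at r = 0.3, a modest gain at 0.5, a large gain at 0.7, and a small loss near 0. The primary outcome, glucose, blood pressure and heart rate are unaffected. Importance is low to moderate, because these are secondary outcomes in an exploratory pilot.

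**What to change.** - **Visits Summary:** at all three visits, give the same hunger, fullness and GI questionnaires once before the drink, beside the baseline finger prick. Check that the GI items make sense at that time. Bring the Research Method sentence on secondary outcomes into line with the actual rating times.
- **Statistical Analyses:** compare supplements on the post-drink rating adjusted for that visit's pre-drink rating, as a covariate and not as a plain change score.
- **Reporting:** give within-supplement change descriptively, stating that without a control visit it also includes elapsed time and continued fasting. Report the observed pre/post correlation for use in later studies.

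The cost is a few minutes of participant time per visit, one error degree of freedom, and a few sentences in the protocol. No extra staff or procedure is needed.

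### With subject as the only random factor, the time-course model tests time-averaged supplement differences against the wrong error term; the resulting error can run in either direction.

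*Combined protocol and SAP*

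**What the plan says.** The Statistical Analyses section gives one model for repeated readings: they will be "analyzed in R using a linear mixed effects model with subjects as a random factor and condition and time as fixed factors". It names no visit (subject×condition) term, no within-visit correlation, no df method and no condition×time term. The only model check is residual Q-Q plots, which show distribution shape, not dependence.

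Under Experimental design, each participant "will participate in three experimental trials with a different ketone supplement in each trial", so a supplement and a visit coincide within a person. β-OHB and glucose are read "at baseline and 15, 30, 60, 90, 120, 180, and 240 minutes after ingestion of the ketone supplement", which is 8 readings per visit. Physiological Measures puts blood pressure and heart rate on the same schedule ("at the same time points as blood samples are collected").

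The primary outcome is the 4-hour β-OHB AUC, one value per visit; its model is not stated separately. Sample Size gives, as one reason for recruiting 12 rather than 6, to "allow for a more nuanced evaluation of differences between ketone supplements". The Hypotheses section says "we do not pose specific hypotheses as to how the ketone supplements will differ".

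**The concern.** Supplement does not change within a visit. A time-averaged difference between supplements is therefore a difference between visits, and should be judged against how much a person's visits vary. A subject intercept alone treats the 24 readings of one person as independent once the person's mean, the condition and the time are allowed for. Two kinds of variation break this:

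- **Visit variation:** anything shared by one visit's readings but not by the person's other visits, such as fasting state, that day's absorption, or serial correlation between close readings.
- **Subject×time variation:** people whose response curves keep their own shape at every visit.

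The first makes the model's standard error for condition too small. The second inflates the residual and makes it too large.

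At stake are P values and confidence intervals for time-averaged supplement differences in β-OHB, glucose, blood pressure and heart rate. Condition is the only supplement term the plan names, and the results are meant to inform later studies.

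**Working it through.** **Plan's own figure.** The documents give none for this test. The N = 6 in Sample Size concerns the rise from baseline. It reproduces under some standard variants (repeated-measures ANOVA with f = 0.5, correlation 0.5 and 6 or 7 time points gives 6) and does not bear on this point.

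**Inputs from the documents.** 12 subjects, 3 visits each, 8 readings per visit, alpha 0.05.

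**Inputs assumed.** Within-subject variance is 1, split into a visit share s and a residual 1 − s. Subject×time variance τ is 0, 0.5 or 1 on the same scale.

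**Degrees of freedom.** Readings: 12 × 3 × 8 = 288. Additive residual: 288 − 1 − 2 − 7 − 11 = 267. With condition×time: 267 − 14 = 253. Subject×condition: 11 × 2 = 22.

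**Standard error of a difference between two supplement means (additive model).**

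- True variance: 2[s + (1 − s)/8]/12. Subject×time cancels, because a person carries it at every visit.
- Model variance: 2·E(MS)/96, with E(MS) = (1 − s) + 8s × 22/267 + 3τ × 77/267, where 77 = 11 × 7.

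At s = 0.10, the true variance is 2 × 0.2125/12 = 0.0354.

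- τ = 0: E(MS) = 0.966, model variance 0.0201, true/model SE = 1.33.
- τ = 0.5: E(MS) = 1.398, model variance 0.0291, ratio 1.10.
- τ = 1: E(MS) = 1.831, model variance 0.0381, ratio 0.96.

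The sign of the error depends on two variances that the documents do not give.

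**Simulated type I error of the omnibus condition test** (additive model, nominal 5%, no supplement effect, 10,000 to 20,000 trials per scenario):

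| Visit share s | τ = 0 | τ = 0.5 | τ = 1 |
|---|---|---|---|
| 0 | 5% | 1.4% | 0.4% |
| 0.05 | 11% | 4% | 2% |
| 0.10 | 18% | 9% | 4% |
| 0.20 | 31% | 18% | 11% |

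Adding condition×time changes these little. One pairwise contrast with τ = 0 gives 9 / 14 / 22% at s = 0.05 / 0.10 / 0.20. The subject×condition error term stays near 5% in every cell.

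**Other assumed structures.**

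- Serial correlation of 0.3 / 0.5 / 0.7 at 15 minutes, with no visit shift and τ = 0: 9.6 / 16.5 / 31.9%.
- Real supplement differences in curve shape (equal means), s = 0.10: the additive test falls from 17.8% to 16.0 / 11.4 / 6.4 / 2.7% as the root-mean-square difference grows to 0.25 / 0.5 / 0.75 / 1.0 within-subject SD. With condition×time in the model it stays at 17.6 to 18.7%.
- Visits that scale the response: Sample Size cites 1.4 ± 0.6 "mM within 30 minutes, and to an average of" 0.5 mM over 4 hours. The assumed curve 0, 0.7, 1.4, 0.9, 0.6, 0.4, 0.2, 0.1 mM has trapezoid average 120/240 = 0.50 mM; the assumed residual SD is 0.2 mM. If subjects also differ in response size, so that the 30-minute SD is 0.6 mM (an assumption about how that spread divides), visit CVs of 10 / 20 / 30% give about 4 / 17 / 35%. Without subject scaling they give about 13 / 28 / 40%, but the 30-minute SD is then only 0.26 / 0.36 / 0.48 mM.

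**Tests not materially inflated under a constant visit shift (s from 0 to 0.30, τ = 0).**

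- AUC per visit: 4.7 to 5.2%.
- 30-minute contrast: 5.1 to 6.4%.
- Supplement difference in change from baseline: 4.8% falling to 2.8%.
- Change from baseline: 5.0% falling to 2.5%.
- Condition×time: 4.9% falling to 0.8%.

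**The case against.** A reader might infer that the planned test is simply anti-conservative. The documents do not support that. They report neither variance, and moderate subject×time variation cancels or reverses the inflation at small visit shares, whether or not condition×time is in the model. Standardised diet, exercise and fasting before each visit may also keep visit variance low. This objection stands, and no direction is claimed here.

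A reader might also infer that the trial's main conclusions are at risk. They are not, under a constant visit shift. The AUC already gives one β-OHB value per visit, the questionnaires are completed once per visit, and objective (b), "To compare changes in blood glucose following acute supplementation with different types of ketone supplements", concerns changes, for which the model is conservative if anything. Both hypotheses concern change from baseline. This too stands, with a limit: if visits scale the response, single-time contrasts are no longer exempt (30-minute contrast 9 / 18 / 24% at visit CVs of 10 / 20 / 30%, without subject scaling).

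Finally, one summary sentence may not describe the full model, and no text says that the condition effect will be the reported comparison. That is fair. But the sentence names the random factor, nothing elsewhere adds another, and that model gives correct error bars only if visit and subject×time variation are both absent or happen to cancel. This is more than missing detail.

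**Conclusion.** The point holds in a limited form. The stated model uses the wrong error term for time-averaged supplement differences: a pooled residual on about 253 to 267 df in place of visit-to-visit variation on 22 df. That follows from the design and from fitting the model as written with independent residuals. The consequence rests on assumed variances: across the table above, a nominal 5% test runs from 0.4% to 31%. Within-visit correlation beyond the subject effect, taken alone, is liberal; correlation that comes only from the subject effect does no harm.

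Importance is modest, because this is an exploratory pilot with no between-supplement hypotheses and a primary outcome that can be analysed per visit. It should still be corrected, because condition is the only supplement term named and the remedy is simple.

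**What to change.** Test time-averaged supplement differences against subject×condition variation, in one of two ways:

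- Add a random intercept for visit nested in subject, with Kenward-Roger or Satterthwaite df, plus a subject×time random term or within-visit serial correlation where the data support it.
- Analyse one mean per visit, with subject as the random factor.

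Keep the chosen error term if condition×time is added. State that the primary AUC is analysed as one value per visit with subject random.

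**Cost.** No new data. Intervals may widen: by about 5% if visits barely vary (t quantiles 2.074 on 22 df and 1.969 on 267 df, ratio 1.05), and by about 40% at a visit share of 0.10 without subject×time variation (1.327 × 2.074/1.969 = 1.40). With 36 visits the visit variance may be estimated at zero, which returns the fit to the subject-only model; the one-mean-per-visit analysis is then safer.
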